### **Evaluation: Efficacy**

The secondary efficacy endpoints are:

Part 2

- Response, as defined by the RAPNO criteria (as determined from MRI assessments, neurological examination, and CSF cytology).
  - ORR calculated as the proportion of all evaluable patients achieving a response (PR or CR) as best overall response at the time of assessment.
- Investigator-assessed DoR, defined as the time from response (CR or PR) to progression.
- PFS defined as the time from first treatment to date of leptomeningeal progression or death from any cause, whichever comes first.
- OS defined as the time from first treatment to date of death.

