### 2.2.2.2. *Part 2*

- PK profile of Lu-DTPA-omburtamab in blood and CSF.
- Response, as defined by the RAPNO criteria (as determined from MRI assessments, neurological examination, and CSF cytology).
  - ORR, calculated as the proportion of all evaluable patients achieving a response (PR or CR) as best overall response at end of Cycle 1 and Cycle 3, EOT Visit, and at each Follow-up Visit.
- Investigator-assessed DoR, defined as the time from first response (CR or PR) to progression.
- PFS, defined as the time from first treatment to date of leptomeningeal progression or death from any cause, whichever comes first.
- OS defined as the time from first treatment to date of death.

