### 4.1. Inclusion Criteria

Patients must satisfy all of the following criteria at the Screening Visit, unless otherwise stated:

1. Histologically confirmed diagnosis of medulloblastoma.
2. SHH, Group 3, or Group 4 according to World Health Organization 2016 classification.
3. Recurrent or refractory to frontline therapy, defined as:
  - a. For Part 1 only: Recurrent (maximum of 2 recurrences) or refractory to frontline therapy. Prior frontline or second-line therapy may involve surgery, craniospinal irradiation, stereotactic radiosurgery, and multi-agent chemotherapy regimens.
  - b. For Part 2 only: Recurrent (maximum of 1 recurrence) or refractory to frontline therapy. Patients with recurrent disease must have received second-line chemotherapy for progressive disease. Prior frontline or second-line therapy may involve surgery, craniospinal irradiation, stereotactic radiosurgery, and multi-agent chemotherapy regimens.
4. Have refractory disease, focal or multifocal recurrent disease, or pure leptomeningeal disease. Cytological or radiographic remission is allowed; however, not simultaneously.
5. Performance status score of 50 to 100, both inclusive, on the Lansky [ $<16$  years] or Karnofsky [ $\geq 16$  years] scales.
6. Aged 3 to 19 years, both inclusive, at the time of the first planned dose of trial treatment.
7. Life expectancy of at least 3 months, as judged by the investigator.
8. Acceptable hematological status prior to first dosing (hematological support is allowed if administered at least 1 week before administration of Lu-DTPA-omburtamab), defined as:
  - a. Hemoglobin  $\geq 8$  g/dL
  - b. White blood cell count  $\geq 1000/\mu\text{L}$
  - c. Absolute neutrophil count  $\geq 1000/\mu\text{L}$
  - d. Platelet count  $\geq 75\ 000/\mu\text{L}$ .

9. Acceptable liver function prior to first dosing, defined as:
  - a. Alanine aminotransferase (ALT) and aspartate aminotransferase (AST)  $\leq 5 \times$  upper limit of normal (ULN)
  - b. Bilirubin  $\leq 1.5 \times$  ULN.
10. Acceptable kidney function prior to first dosing, defined as:
  - a. Estimated glomerular filtration rate (eGFR)  $>60$  mL/min/1.73 m^2, calculated by the 2009 revised Bedside Schwartz Equation ([Appendix 4](#)).
11. Written informed consent from legal guardian(s) and/or child obtained in accordance with local regulations. Pediatric patients must provide assent as required by local regulations.

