## 7.3. Efficacy Assessments

### 7.3.1. Progression-free Survival

Progression-free survival (PFS) will be assessed by MRI, neurological examination, and CSF cytology. As detailed in the RAPNO criteria ([Appendix 6](#)), progression is defined when any of the PD criteria are met. The timeframe for assessment of PFS will be from the first treatment dose of Lu-DTPA-omburtamab to time of disease progression or death from any cause. Patients lost to follow-up without any sign of progression will be censored at the date of last PFS assessment.

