### 7.3.2. Response Evaluation, Overall Response Rate, and Duration of Response

Response, as defined by the RAPNO criteria (Warren et al. 2018; see Appendix 6) will be assessed in Part 1 at the EOT Visit. In Part 2, response will be assessed at end of Cycle 1 and Cycle 3, EOT Visit, then 26, 39, and 52 weeks post first dose, followed by 78 and 104 weeks post first dose of Lu-DTPA-omburtamab. Notably, objective response and stable disease requires that all criteria are met, while progression is defined when any of the PD criteria are met.

The ORR will be calculated from baseline MRI scans and from scans after the dosing of Lu-DTPA-omburtamab using 2 methods: firstly, by considering MRI data, neurological examination, and CSF cytology data together (RAPNO criteria); secondly, by considering CSF cytology data only. ORR will be defined as the proportion of all evaluable patients achieving a CR or PR as best overall response at the time of assessment.

Investigator-assessed DoR (Part 2) is defined as the time from response (CR or PR) to progression. Patients without any sign of progression will be censored at the date of their last PFS assessment.

In Part 1 and Part 2, the baseline CSF cytology assessment must be completed within 3 weeks prior to the first Lu-DTPA-omburtamab treatment dose infusion. Cerebrospinal fluid cytology should be assessed as positive/negative. Cerebrospinal fluid cytology will be assessed in Part 1 at screening, the EOT Visit, and in Part 2 at screening, end of Cycle 1 and Cycle 3, EOT Visit, and at each Follow-up Visit.

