### 8.3. General Considerations

Summary statistics, listings, and statistical analyses will be performed for patients included in the relevant analysis sets.

For continuous data, summary statistics will include the arithmetic mean, arithmetic standard deviation, median, minimum, maximum, and number. For log-normal data (e.g., the PK parameters, the activity-time curve and elimination half-life of absorbed doses to CSF and

blood), the geometric mean and geometric coefficient of variation will be presented instead of mean and SD. For categorical data, frequency counts and percentages will be presented. Data listings will be provided for all patients up to the point of withdrawal, with any patients excluded from the relevant analysis set highlighted. For the calculation of summary statistics, listings, and statistical analysis, unrounded data will be used.

For the time to event efficacy endpoints, patients who do not have an event will be censored at the date of their last evaluation. If partial dates are present, a conservative approach will be used. If partial dates are present for efficacy time to event endpoints, missing months and/or days will be imputed as January and the first day of the month, respectively. AEs with a missing start date or time that leads to ambiguity in whether the AE is treatment-emergent will be considered treatment-emergent. It is unlikely that other missing of safety data will occur in the targeted patient population, but in case it happens the data will not be imputed.

When the last patient in Part 1 has completed the EOT visit, all available data for that part will be reported.

For Part 2, full efficacy and safety analyses will be performed when the last patient completes week 52 assessments, dies, or is lost to follow up. An updated long term survival analysis will be performed when the last patient has reached the 104 week visit, dies, or is lost to follow-up.

Data analysis will be performed using SAS® Version 9.3 or higher.

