### **8.4.1. Part 2 Efficacy Analysis**

Overall survival at 1 and 2 years post first dose will also be estimated using Kaplan-Meier methods. Patients not deceased will be censored at the last date known to be alive. The median PFS time and the proportion of patients without PFS events at 1 and 2 years post first dose will be estimated using Kaplan-Meier methods, along with their 95% confidence intervals. Results will be displayed in Kaplan-Meier plots. The ORR according to RAPNO criteria (MRI, neurological examination, and CSF cytology), as well as according to CSF cytology alone, will be assessed. The 95% confidence intervals will be calculated using the Clopper-Pearson exact methodology. Investigator-assessed DoR will be estimated using Kaplan-Meier methods. The median DoR and corresponding 95% confidence interval will be calculated.

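### PFS has two conflicting event definitions and the analysis section does not choose between them; DoR leaves out death, so a responder who dies without documented progression is censored

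*Combined protocol and SAP*

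**What the plan says.** **PFS, endpoint sections.** Section 2.2.2.2 reads "PFS, defined as the time from first treatment to date of leptomeningeal progression or death from any cause, whichever comes first". The synopsis (Evaluation: Efficacy) gives the same event.

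**PFS, assessment section.** Section 7.3.1 assesses PFS by MRI, neurological examination and CSF cytology, refers to Appendix 6, and states that "progression is defined when any of the PD criteria are met". The clock runs to disease progression or death, with no leptomeningeal restriction.

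**PFS, analysis section.** Section 8.4.1 plans to estimate "The median PFS time and the proportion of patients without PFS events at 1 and 2 years post first dose" by Kaplan-Meier. It does not define a PFS event, and neither do the synopsis statistical methods or Section 8.3.

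**Population.** Inclusion criterion 4 (Section 4.1) requires patients to "Have refractory disease, focal or multifocal recurrent disease, or pure leptomeningeal disease".

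**DoR.** Section 7.3.2 states: "Investigator-assessed DoR (Part 2) is defined as the time from response (CR or PR) to progression". Section 2.2.2.2 and the synopsis also name progression only. On censoring, Section 7.3.2 adds: "Patients without any sign of progression will be censored at the date of their last PFS assessment". The general rule in Section 8.3 is that "patients who do not have an event will be censored at the date of their last evaluation". Neither rule makes an exception for death.

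**The concern.** The two PFS events are not the same. Under Appendix 6, progression can be growth of a measurable brain lesion, any new brain or spine tumor, unexplained clinical deterioration, or a new site outside the CNS. None of these has to be leptomeningeal. Appendix 6 has no leptomeningeal category either, so the narrower event has no working criterion.

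Other sections widen the gap. Section 4.3.2.1 stops trial treatment for disease progression of any kind, and Section 6.1 allows other anti-cancer therapy after the EOT Visit. No rule censors PFS when new therapy starts. Under Section 2.2.2.2 a patient could therefore progress focally, leave treatment, start another therapy and still count as progression-free.

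The trial is open-label and single-arm, and Section 8.9 foresees ad hoc interim analyses for regulators. An unsettled definition leaves room to choose the event after data have been seen.

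For DoR, censoring deaths treats those responders as if they could still have progressed later. That biases duration upward and makes DoR inconsistent with PFS in the same patients.

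**Working it through.** **1. The plan's own figures.** Nothing is sized on PFS or DoR. The Part 2 figures in Section 8.1 reproduce: 1 − 0.9^24 = 0.920 (stated as at least 90%), and the Clopper-Pearson lower limit for 5/20 is 8.66% (stated as 9%). The expected 5 responders out of 20 evaluable patients are the likely DoR set.

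**2. The definitions side by side.**

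| Patient's first event | Synopsis and 2.2.2.2 PFS | 7.3.1 PFS | DoR as written (responders) |
|---|---|---|---|
| Leptomeningeal progression | event | event | event |
| Focal growth or new focal lesion | not an event | event | event |
| New site outside the CNS | not an event | event | event |
| Death with no sign of progression | event | event | censored |

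The DoR column assumes that progression means any RAPNO PD, as Section 7.3.2 says. The last cell is inferred from Sections 7.3.2 and 8.3 together; no sentence in the protocol says that deaths are censored.

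**3. Possible size for PFS (illustration).** Assumptions, none of them in the documents:
- the hazard of any RAPNO PD or death is constant, with 1-year PFS of 30%, so L = −ln(0.30) = 1.204 per year;
- a share g of first failures is non-leptomeningeal progression;
- after such a failure, the hazard of leptomeningeal progression or death is k = mL.

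Under the leptomeningeal-only definition, 1-year PFS is

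S(1) = 0.30 + g·L·(e^(−k) − e^(−L))/(L − k), or 0.30 + g·L·0.30 when k = L.

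Example with g = 0.2 and m = 2: 0.30 + 0.2 × (0.30 − 0.09) = 0.342.

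| g | m = 1 − g | m = 1 | m = 2 | m = 3 |
|---|---|---|---|---|
| 0.2 | 38.2% | 37.2% | 34.2% | 32.7% |
| 0.5 | 54.8% | 48.1% | 40.5% | 36.8% |

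The column m = 1 − g supposes that non-leptomeningeal progression does not raise the later hazard at all. It is the most favourable case shown. The columns m = 2 and 3 are more plausible for a disease that Section 3.2 describes as having a poor prognosis.

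**4. Possible size for DoR (illustration).**
- *Constant hazard.* If a fraction f of failures are deaths without documented PD and these are censored, the median is inflated by 1/(1 − f): 1.05, 1.11 and 1.25 for f = 5%, 10% and 20%.
- *Five responders, one censored, no other censoring.* The Kaplan-Meier median (first time with S ≤ 0.5) moves from the 3rd to the 4th ordered time when the censored time is 2nd or 3rd in order, so in 2 of 5 positions. With times of 4, 6, 9, 12 and 15 months the median is 9; censoring at 6 or at 9 makes it 12. If the last assessment before the 6-month death fell before month 4, the censored time is 1st in order and the median stays 9.
- *Estimability, same setting.* With one or two censored, the median is always estimable. With exactly three censored it is lost in 2 of 10 orderings.
- *With administrative censoring.* Simulation of 5 responders, exponential median 9 months, deaths censored at the previous 3-monthly visit. With 24 months of follow-up from response, the median is inestimable in about 3% of runs if deaths are events, and in 4%, 6% and 10% if deaths are censored at f = 5%, 10% and 20%. With 11 months of follow-up and f = 10%, the figures are about 37% and 42%.

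**The case against.** **PFS.** Section 7.3.1 is the dedicated assessment section and the only place with operational criteria, and Section 7.3.2 repeats its any-PD rule. A reader could take it as governing, in which case nothing is inflated. A leptomeningeal endpoint might also be deliberate for an intraventricular agent aimed at small-volume disease, and newly positive CSF cytology and progression of nonmeasurable disease offer partial ingredients for a criterion. This shows how the conflict could be settled, but no section settles it: two current sections state one event, a third states another, and Section 8.4.1 is silent. Post hoc selection is a possibility, not something the documents show.

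**DoR.** Death is unmentioned rather than explicitly censored. Unexplained clinical deterioration is itself PD (Section 7.1.5 and Appendix 6), so most disease deaths would be preceded by an event. What remains is mainly abrupt, toxic or unrelated deaths among a handful of responders, and those deaths still count in PFS and OS. This stands, and it makes DoR the smaller half of the point.

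**Numbers.** Every PFS rate and share is assumed. The 24-month, 3-monthly simulation is also more generous than the protocol: visits stop at 104 weeks after first dose and become 26-weekly after week 52, and the full efficacy analysis comes at week 52. With shorter follow-up, administrative censoring is the main cause of an inestimable median, and death handling adds about 5 percentage points (37% to 42%). This stands as a limit on the illustration; the direction of the bias is unchanged.

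**Conclusion.** The point holds. PFS has two incompatible event definitions in current text and the analysis section does not choose. Applied literally, the DoR rules censor a responder who dies without documented progression.

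The PFS effect depends on which definition is used. It is nil if Section 7.3.1 governs. If the leptomeningeal wording is used, 1-year PFS is overstated relative to Section 7.3.1: on the assumed 30% base, by about 3 to 8 percentage points at a 20% non-leptomeningeal share and about 7 to 25 points at a 50% share. The upper ends require that non-leptomeningeal progression carries no added later risk. The DoR median is inflated by 5% to 25% for f between 5% and 20% under a constant hazard, and one death among five responders can shift it by one ordered time.

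Both endpoints are secondary and descriptive, so no hypothesis test, sample size or dose decision is affected. The text should be fixed, but the trial's primary conclusions do not depend on it.

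**What to change.** 1. State one PFS event in the synopsis and Sections 2.2.2.2, 7.3.1 and 8.4.1: progression by any Appendix 6 PD criterion, or death from any cause. Section 7.3.1 already says this.
2. If leptomeningeal progression is of separate interest, add time to leptomeningeal progression as a supplementary endpoint, with a written criterion and a stated handling of non-leptomeningeal progression and death.
3. Define DoR as the time from first CR or PR to progression or death from any cause, in the synopsis and Sections 2.2.2.2 and 7.3.2. Censor at the last adequate response assessment only if neither has occurred, and say what makes an assessment adequate.
4. Align the censoring sentences in Sections 7.3.2 and 8.3 with these definitions.

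The cost is wording only, with no new data collection. It is best done before any Part 2 efficacy data are analysed, including ad hoc interim analyses. The one downside is that reported PFS and DoR may look slightly less favourable.

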### 3. INVESTIGATION PLAN

#### 3.1. Overall Trial Design and Plan Description

This is a Phase I/II, open-label, safety and efficacy trial in pediatric and adolescent patients (3 to 19 years) with recurrent or refractory medulloblastoma. The trial will be conducted in 2 parts:

- Part 1: a dose-escalation phase with a 3+3 sequential-group design (except for the first dose level, which will consist of a single patient only) of five planned dose levels, and in which up to 25 patients will receive a maximum of two 5-week cycles of treatment with intracerebroventricular Lu-DTPA-omburtamab. Patients will receive a dosimetry dose in Week 1. Treatment doses will follow in Week 2 of the first cycle, and on the first day of Cycle 2. Adjustments to the dosing schedule will be accommodated on a patient-by-patient basis depending on the clinical condition of the patient. A Data Monitoring Committee (DMC) will review the safety data from previous dose levels and provide recommendations on whether dose escalation should continue. The MTD and/or RP2D will be determined.
- Part 2: a cohort-expansion phase in which approximately 24 patients with recurrent or refractory medulloblastoma will receive a maximum of five cycles of treatment with intracerebroventricular Lu-DTPA-omburtamab at the RP2D determined in Part 1.

Patients participating in Part 1 are not permitted to participate in Part 2.

Lu-DTPA-omburtamab will be administered via an indwelling intracerebroventricular access device (e.g., Ommaya reservoir). To avoid an additional procedure and burden to the patient, it can be considered to place the intracerebroventricular access device in connection with any tumor resection procedure that may be performed before entry into the trial. In this case, the informed consent form (ICF) must be signed before the tumor resection.

Potential participants will be screened to assess their eligibility to enter the trial within 29 days prior to the first Lu-DTPA-omburtamab dose; however, signing the ICF and placement of the intracerebroventricular access device is allowed earlier than this. Final assessment of the eligibility criteria is done prior to first dose. In Part 1 Cycle 1, the dosimetry and treatment doses should be administered under controlled conditions with inpatient care for at least 24 hours after investigational medicinal product (IMP) administration. As a routine precaution, patients must be monitored during the infusion and with close observation for two hours after the infusion with readily available resuscitation equipment and access to emergency units. Staff should be qualified in resuscitation and the physician must be readily accessible for assistance during the day of the infusion. The infusion reservoir must be flushed with human serum albumin and CSF after each infusion. The patient must be observed regularly, and the patient can be discharged after 24 hours if no safety issues are observed.

In Part 1 Cycle 2 and in Part 2 Cycle 1 to 5, patients can be treated in an outpatient setting or can be admitted as inpatients for infusions; however, all patients should be observed for a minimum of 2 hours after end of each infusion and can be released if no safety issues are observed.

An external DMC will be established to review the data and recommend upon dose escalation ([Section 4.4](#)).

Local safety instructions for storage and handling of radioactive drug products must be strictly followed. Radiation safety precautions may include patient isolation and the use of lead shielding, or designated rooms to ensure that the dose rate in the surrounding areas meets regulatory requirements.

A detailed Schedule of Assessments is included in [Appendix 3](#).

### 3.1.1. Part 1 (Dose-escalation Phase)

Part 1 will comprise 1 dose level consisting of a single patient followed by additional dose levels that use a 3+3 design (see [Figure 1](#)).

In the first 5-week treatment cycle, a 5 mCi dosimetry dose will be administered on Day 1 and a treatment dose (according to the assigned dose level, as listed below) will be administered on Day 8 (see [Figure 1](#) for a schematic of a treatment cycle in Part 1). However, if a patient experiences a Grade 3 or 4 non-hematologic AE (including an AE considered to be a Grade 3 or 4 nervous system disorder) or other DLT after receiving the dosimetry infusion, the treatment dose will not be administered, and the patient will be discontinued from trial treatment. If the dosimetry dose of 5 mCi turns out to deliver a too low acquisition of radioactivity count (see [Section 7.2](#)), the dosimetry dose will be increased to 10 mCi for subsequent patients, at the sponsor's discretion.

A fixed mass dose of approximately 1 mg DTPA-omburtamab will be labelled with increasing radioactivity doses. This mass dose was selected based on the clinical experience with iodine-labelled omburtamab, in which the same mass dose has been shown to be stable and to support clinical use in concentrations up to 100 mCi/ml. The planned radioactivity dose levels are:

- Dose Level 1 (1+2 patients): 10 mCi
- Dose Level 2 (3+3 design): 25 mCi
- Dose Level 3 (3+3 design): 50 mCi
- Dose Level 4 (3+3 design): 65 mCi
- Dose Level 5 (3+3 design): 85 mCi.

A maximum of 1 additional intermediate dose level may be added to the trial if warranted based on the findings from previous dose levels (see [Section 3.1.1.1](#)).

[figure not shown]
Patients who are not discontinued from treatment (according to the criteria in [Section 4.3.2](#)) will be eligible for a second treatment cycle at the same dose administered in the first cycle. The second treatment cycle will not include a dosimetry dose but will instead consist of a treatment dose on Day 1 of the cycle.

In Part 1, the patients will receive a maximum of 2 treatment cycles. Patients who do not experience a DLT will be eligible for Cycle 2 dosing at the same dose administered in Cycle 1. Cycle 2 dosing will not include a dosimetry dose but only a treatment dose on the first day of the cycle.

Patients will undergo monitoring for AEs; routine safety assessments (vital signs, clinical chemistry, hematology); whole-body planar gamma camera (and SPECT, if possible) scans for dosimetry measurements; CSF sampling for total protein, glucose, ctDNA (if the patient has given informed consent to this analysis), and cell count; blood and CSF draws for PK; and blood and CSF draws for ADA analysis and for potential culture (only in case of elevated body temperature); neurological assessments and radiographical investigation for evaluation of neurological AEs; and assessment of performance status (Lansky [ $<16$  years] or Karnofsky [ $\geq 16$  years] scales). Efficacy assessments include brain and spine MRI, CSF sampling for cytology, and neurological examination.

Patients will return for an EOT Visit 5 to 6 weeks after the last dose of Lu-DTPA-omburtamab to assess safety. End of Trial data will be entered to the eCRF. In addition, all patients who are dosed with Lu-DTPA-omburtamab will enter a post-trial monitoring period in which they will be regularly (e.g., yearly) followed up for secondary malignancies (see [Section 7.4.5.3](#)) for at least 10 years after end of trial, or until death, if sooner. This post-trial monitoring can be conducted by contacting the patient or the general practitioner, the referral site (if applicable), or by checking medical records or other sources.

## Figure 1: Trial Design – Part 1 Cycle 1

Abbreviations: DMC = Data Monitoring Committee; N = number of patients.

\* If the dosimetry dose of 5 mCi turns out to deliver a too low acquisition of radioactivity count (see [Section 7.2](#)), the dosimetry dose will be increased to 10 mCi for subsequent patients, at the sponsor's discretion.

After Cycle 1, the treatment dose will be administered on Day 1 (Week 1) of the cycle.

